**Outcome measures**

All outcome data will be collected at baseline, at post-treatment/control period follow-up, and as long-term follow-up before the youth leaves the SiS home (this time point may vary several months).

*Ratings by independent blinded assessor*

Clinical Global Impression-Improvement (CGI-I): Scale for rating of global improvement or worsening of problems/symptoms (score range 1-7; 1 very much improved, 7 very much worse) (Guy 1976).

Clinical Global Impression-Severity (CGI-S): Scale for rating of global problem/symptom severity (score range 1-7; 1 no problems, 7 extreme problems) (Guy 1976).

*Ratings by contact persons*

Broset Violence Checklist (BVC) - ratings of daily problem behaviors

SNAP – IV – Swanson, Nolan and Pelham scale. Rating scale for ADHD- and oppositional symptoms (Swanson 1992).

ECBI - Eyberg Child Behavior Inventory – rating scale for challenging behaviors (Eyberg & Pincus 1999).

RPQ - Relationship Problems Questionnaire – rating scale for relationship problems (Minnis et al 2002)

*Youth self-ratings*

BYI - Beck Youth Inventories - interview about symptoms of depression, anxiety, irritability, challenging behavior, self-image (Beck et al 2005).

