**Screening visit at GNC – or videolink:**

Coordinator and contact persons from the youth home together with the GNC *blinded assessor* assess the screening results and inclusion/exclusion criteria.

*Randomisation*

Computer-generated unstratified block-randomisation (blocks of 4-8 youth) 1:1 to treatment or control, is performed by independent project leader

*Primary outcome*

- CGI-I rated by blinded assessor

*Secondary outcomes* (change from baseline measured with the following instruments):

- CGI-S rated by blinded assessor
- Ratings by the youth's contact person:
  - BVC (number/intensity of problem situations)
  - SNAP-IV (ADHD and oppositional symptoms)
  - ECBI (challenging behaviors)
  - RPQ (relationship problems)
- BYI (youth self-ratings)
- Therapist-ratings with the Problem Rating Scale (measures how many problem situations could be wholly or partially solved).

*Active group:* Contact person and youth learn and practice the method at weekly visits with therapist for 10 weeks, and practice problem solution strategies in everyday life between visits. Therapists will be given supervision and support once monthly from therapists in our GNC research team.

*Control group:* Receives "treatment as usual" during the 10-week control period, and thereafter 10 weeks of PR-ESSENCE-training.

*Continuous evaluations during the trial*

- BVC-ratings of problem behaviors will be made daily during the whole trial, by contact persons at the youth home (ward and school). Weekly results will be collected.
- With the Problem Rating Scale, the therapists will at each visit rate the number of problem situations which have been wholly or partially solved.

*Statistical plan*

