Sample size calculation indicates that with power 0.80 and significance level of .05, a sample of 52 participants would be required to detect an effect size (Cohen's *d*) of 0.7, which may be considered as a clinically meaningful effect. Previous research has shown larger effect sizes on the primary outcome measure CGI-I. Primary and secondary efficacy analyses will be performed on all randomized subjects (Intention-to-Treat (ITT) population) with baseline values carried forward to endpoint for dropouts, on the Full Analysis Set (FA set) defined as all randomized subjects with any baseline and any end of treatment measurements, and on the Per Protocol population (subjects who completely followed the protocol). Analyses of covariance, covarying for baseline values, will be used to compare posttreatment assessment scores in the PR-ESSENCE versus control groups. For comparison between the groups Mantel-Haenszel chi-square test will be used for ordered categorical variables, Fisher's exact test for dichotomous variables and Pearson chi-square for non-ordered categorical variables. For dichotomous variables the risk difference with 95% CI and the risk ratio with 95% CI will be presented. Effect Sizes (ES) will be calculated as the difference in mean scores between PR-ESSENCE group and controls, divided by the pooled standard deviation. The distribution of continuous and interval scaled variables will be reported as mean, SD, median, minimum and maximum and distribution of categorical variables as numbers and percentages.

*Dissemination*

Our research team will collect and analyze all data, write research reports, publish the study results on group level in international journals, and present results on national and international conferences. Education and supervision on the method can be provided to other SiS youth homes on demand.

*Future perspectives*

The GNC trial provided new knowledge about solutions for behavior problems and conflict management. We hope that PR-ESSENCE training in SiS Youth Homes can give long-term improvements in self-regulation abilities and conflict solutions, and thereby prevent challenging, disruptive and antisocial behaviors. If lasting improvements in problem-solving abilities and

interaction could reduce violence, drug use and criminality, this would give large psychological and economic gains for families and society.

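### For the secondary scales with a baseline, the effect size is not tied to the ANCOVA it accompanies: it reads as an unadjusted Cohen's d, is less precise, and has no promised confidence interval.

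*Combined protocol and SAP*

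**What the plan says.** All of the relevant analysis text is in the *Statistical plan* of the combined protocol and SAP.

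- **Test:** "Analyses of covariance, covarying for baseline values, will be used to compare posttreatment assessment scores in the PR-ESSENCE versus control groups".
- **Effect size:** "Effect Sizes (ES) will be calculated as the difference in mean scores between PR-ESSENCE group and controls, divided by the pooled standard deviation". The sentence mentions no adjusted or least-squares means. It does not say whether the means are of post-treatment or change scores, or which SD is pooled.
- **Intervals:** "For dichotomous variables the risk difference with 95% CI and the risk ratio with 95% CI will be presented". No interval is promised for a mean difference or an effect size.
- **Ordered categories:** a "Mantel-Haenszel chi-square test will be used for ordered categorical variables". The plan does not say whether CGI-I falls under this test or under the ANCOVA.

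The primary outcome is "CGI-I rated by blinded assessor". *Outcome measures* describes this instrument as a "Scale for rating of global improvement or worsening of problems/symptoms", so it has no pre-treatment value. The secondary outcomes are listed as "change from baseline measured with the following instruments". *Outcome measures* has all outcome data collected at baseline, so a baseline is available for CGI-S, BVC, SNAP-IV, ECBI, RPQ and BYI. The Problem Rating Scale counts situations solved during treatment and is left out here.

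**The concern.** For a scale with a baseline, the plan would print an ANCOVA p-value beside an effect size that, on its plain reading, ignores the baseline. ANCOVA removes chance imbalance in the baseline score; a plain difference in means keeps it. The design leaves such imbalance to chance: *Design* plans 60-70 youth, about 30-35 per arm, and *Randomisation* is unstratified.

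Two things are at stake. The effect size is less precise than the analysis already planned. In a given trial it can also differ from the ANCOVA result by a few tenths of an SD, with no interval to show how uncertain it is. Because the sentence fixes neither the type of score nor the SD, several effect sizes would satisfy it, and the choice could be made after the data are seen.

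**Working it through.** **The plan's own figure.** The plan says that "with power 0.80 and significance level of .05, a sample of 52 participants would be required" for d = 0.7. With n per arm = 2(z_alpha + z_power)²/d²:

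- One-sided: 2(1.645 + 0.842)²/0.49 = 25.2, so 26 per arm and 52 in total. This matches.
- Two-sided: 2(1.960 + 0.842)²/0.49 = 32.0, so 33 per arm and 66 in total (68 by the t-test). This does not match.

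Sidedness is not stated. That is a separate matter, and the change proposed here leaves 52 as it is.

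**Inputs.** From the documents: 30 and 35 per arm (60-70 randomised 1:1), true d = 0.7, ANCOVA on the post-treatment score. Assumed, because the documents give no value: baseline-to-post correlation r = 0.3, 0.5 or 0.7. Also assumed: normal scores, equal SDs and complete data.

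**Formulas.** Let D_post and D_base be the differences in arm means, b the pooled within-arm slope, and S the pooled post-treatment SD.

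- Unadjusted ES = D_post / S
- Adjusted ES = (D_post − b·D_base) / S
- Gap = b·D_base / S, with SD of about r·√(2/n)

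**Size of chance imbalance.** At n = 30, √(2/30) = 0.258. An absolute imbalance above 0.3 SD then has probability 2·[1 − Φ(0.3/0.258)] = 25%. At n = 35, √(2/35) = 0.239 and the probability is 21%.

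**Gap by formula at n = 30.** 1.96 × r × 0.258 = 0.15, 0.25 and 0.35 for r = 0.3, 0.5 and 0.7.

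**Gap by simulation** (20,000 trials per setting, d = 0.7). The values run slightly higher at low r because the slope is estimated.

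| | r = 0.3 | r = 0.5 | r = 0.7 |
|---|---|---|---|
| 95% of gaps within, n = 30 | 0.17 | 0.26 | 0.35 |
| 95% of gaps within, n = 35 | 0.16 | 0.24 | 0.33 |
| Gap above 0.2, n = 30 | 3% | 12% | 27% |
| SD of unadjusted ES, n = 30 | 0.269 | 0.268 | 0.270 |
| SD of adjusted ES, n = 30 | 0.260 | 0.237 | 0.201 |
| Variance ratio, adjusted/unadjusted | 93% | 78% | 55% |
| Two-sided 5% significance differs, n = 30 | 8% | 14% | 21% |
| Opposite sides of 0.7, n = 30 | 9% | 16% | 24% |

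The variance ratios are squared ratios of the SDs above, for example (0.201/0.270)² = 0.55. Both effect sizes average about 0.71.

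**If the means are of change scores.** The gap becomes (1 − b)·D_base / S, so it is largest where r is low. At n = 30, 95% of gaps lie within 0.38, 0.28 and 0.17. If the pooled SD is that of the change scores, √(2(1 − r)) = 1.18, 1.00 and 0.77, the same true effect averages 0.60, 0.71 and 0.92.

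**If the SD is the ANCOVA residual SD.** That SD is √(1 − r²) = 0.95, 0.87 and 0.71 of the score SD, so a true 0.7 becomes about 0.73, 0.81 and 0.98. The SD therefore has to be named as well.

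**The case against.** The strongest reply is that a mean difference over the pooled SD is the standard Cohen's d, the metric used in the sample-size statement, and that it is not biased under randomisation. That is correct: the two versions average the same and differ only in precision. At r = 0.3 the gain is small, with a 7% reduction in variance and a gap above 0.2 in only 3% of trials. The plan also does not rule out an interval for continuous outcomes; it only fails to promise one.

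A reader might draw four stronger conclusions that the documents do not support.

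- **That the trial's headline result is affected.** CGI-I has no baseline score, so a gap between an unadjusted and an own-baseline-adjusted effect size cannot arise on it. Its p-value may not come from an ANCOVA at all, since its test is not specified. The sentence after the d = 0.7 statement speaks of CGI-I, so that benchmark attaches most naturally to the primary outcome.
- **That the plan prescribes raw post-treatment means.** This is the plain reading, but the sentence does not say so, and the secondary outcomes are listed as changes from baseline.
- **That the effect size could point the opposite way from the ANCOVA.** At d = 0.7 and 30 per arm the signs differ in only about 0.2-0.4% of trials. The rate is 10-25% when the true effect is zero, where the sign carries no meaning.
- **That adjustment would stop the estimate crossing 0.7 by chance.** With a true d of 0.7, the adjusted effect size also falls below 0.7 in about half of trials.

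These limits narrow the point to the secondary scales. They do not explain why a less precise effect size should accompany the ANCOVA when the adjusted difference is already available. The change-score reading does not remove the mismatch either, as the working shows.

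**Conclusion.** The point holds for CGI-S, BVC, SNAP-IV, ECBI, RPQ and BYI. On these scales the plan's effect size is not linked to the planned ANCOVA estimate, most naturally reads as unadjusted, and carries no promised interval. The loss is one of precision and consistency, not bias. How large it is depends on a correlation that the documents do not give: over r = 0.3 to 0.7 it runs from minor to substantial, so scale-specific correlations would be needed to narrow the range. The figures also rest on normal, complete data; carrying baseline values forward for dropouts would alter the correlation.

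None of these figures applies to CGI-I. This is a free improvement to the plan. It is not an error that threatens the primary conclusion.

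**What to change.** In the *Statistical plan*, replace the effect-size sentence with text to this effect: for each outcome with a baseline value, the effect size is the ANCOVA-adjusted mean difference (PR-ESSENCE minus control) divided by a named SD, and the adjusted difference and the effect size are both reported with 95% confidence intervals. The pooled unadjusted post-treatment SD would serve. The residual SD should not be used, because it inflates the figure relative to an ordinary Cohen's d.

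Add a separate statement for CGI-I giving its test, any covariate and its effect size. Baseline CGI-S is already collected and can serve as the covariate. That is a decision about the primary analysis, to be fixed before outcome data are seen. The precision gains above should not be claimed for it, because the correlation of baseline CGI-S with CGI-I is unknown.

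The cost is a few lines of text. The ANCOVA already yields the adjusted difference and its standard error, no new data are needed, and the sample size does not change.
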